The current project seeks to evaluate ways to improve outcomes for low-education, uninsured or Medicaid-eligible smokers who do not quit with standard quit line treatment. The current proposal will use an efficient factorial design to evaluate four evidence-based strategies to improve follow-up WTQL care offered to socioeconomically disadvantaged callers who report smoking four months following initial WTQL treatment comprising a single counseling call and 2-week supply of a single nicotine replacement therapy. These strategies include: increasing the intensity of nicotine replacement medication (among those medically cleared to use such medications), increasing the intensity of WTQL counseling, helping callers enroll in an evidence-based smoking cessation texting support program (SmokefreeTXT), and offering moderate financial incentives for engagement in counseling and SmokefreeTXT. This evaluation will identify which program enhancements, and which combination of program enhancements, improve abstinence rates in this high-priority and high-risk segment of the population served by the WTQL.

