### **II. GOALS/AIMS**

The overarching aim of the proposal is to evaluate ways to enhance quit line treatment for low-income smokers in terms of abstinence, costs, and reach. The specific aims of the project are listed below.

1. To assess the main and interactive effects of the four experimental factors (see below) on biochemically confirmed, 7-day point-prevalence abstinence at 6-month follow-up among low-education, uninsured, or Medicaid-eligible smokers who relapse following a standard WTQL intervention. Secondary abstinence outcomes are self-reported point-prevalence abstinence 12-weeks post-quit and continuous abstinence between months 1 and 6 post-quit.

Factors	Levels
1. Quit line counseling intensity	1. 1 vs. 4 proactive counseling calls
2. Nicotine replacement therapy (NRT) intensity	2. Patch (2 wks) vs. Patch+ Lozenge (4 wks)
3. SmokefreeTXT text messages	3. Proactive enrollment vs. none
4. Financial incentives for treatment engagement	4. \$30-\$150 vs. none
2. To evaluate the cost-effectiveness of each intervention component overall and in the context of the other components (i.e., additive and interactive effects and their impact on cost-effectiveness). The aim is to develop data to inform future quit line care planning and policy.	
3. To identify demographic and smoking history moderators of treatment engagement and response and mediators of intervention effects (e.g., treatment engagement) on 6-month abstinence. This aim will identify sub-populations that may not benefit equally from enhanced WTQL services and will suggest ways to refine the treatments to enhance their efficacy.	

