## Analysis Plan

To assess Aim 1, we will test the main and interactive effects of counseling intensity, NRT intensity, SmokefreeTXT, and engagement incentives on biochemically confirmed, 7-day point-prevalence abstinence at 6-month follow-up. Secondary abstinence outcomes are self-reported point-prevalence abstinence 12-weeks post-quit and continuous abstinence between months 1 and 6 post-quit.

*Measures, Populations and Analysis:*

Data for the primary, abstinence-focused analyses will include randomized levels of the treatment factors and their interactions as independent variables, binary abstinence outcomes based on self-reported abstinence (at 12-week follow-up) and biochemical verified abstinence (at 26-week follow-up only) as the dependent variables, and covariates such as demographics and smoking history collected at registration or enrollment.

The population will be the eligible, consented, enrolled subjects who were randomized to treatment. Participants who were randomized but did not complete the study will be included in analyses (unless they requested that their data not be used upon withdrawal from the study). Analyses will occur in the full intent-to-treat sample.

Logistic regression analyses will be used to estimate intervention main and interactive effects on binary abstinence outcomes. Both unadjusted models and models adjusted for covariates will be run. Separate models will be run for different outcomes (e.g., biochemically confirmed abstinence at 26-weeks post-quit, self-reported abstinence at 12 weeks post-quit, continuous abstinence between 4 and 26-weeks post-quit) under different assumptions regarding missing abstinence data (e.g., assuming all missing are smoking, assuming 80% of missing are smoking, using multiple imputation).

*Data Sources and Collection:* The primary outcome data will be collected by UW-CTRI via telephone follow-up interview and in-person, mailed, or emailed validation of abstinence via CO breath testing and/or urinary or salivary cotinine testing. Covariates will be assessed by WTQL staffers at registration or enrollment and transferred securely to UW-CTRI for analysis.

To assess Aim 2, we will evaluate the costs and cost-effectiveness of each intervention component overall and in the context of the other components (i.e., additive and interactive effects and their impact on cost-effectiveness).

*Measures, Populations and Analysis:*

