Cost data will come from: research participants who will report on their out-of-pocket costs of tobacco and treatment and health care utilization at enrollment and follow-up; Optum who will report on intervention delivery, supply, and support costs; SmokefreeTXT who will report minute/data use costs associated with cumulative message volume and the estimated cost per user for the program; and from public data sources (on the costs and savings associated with cessation and continued smoking).

The population will be the eligible, consented, enrolled subjects who were randomized to treatment. Participants who were randomized but did not complete the study will be included. Analyses will occur in the full intent-to-treat sample whenever possible, using model estimation that permits missing data. Utilization rates have important implications for intervention costs, so both low and high utilizers of intervention components will contribute important data to these analyses.

Cost and efficacy data (abstinence outcomes assessed in Aim 1) will be used to estimate the costs per verified quit by treatment condition, in accordance with recommendations for cost-effectiveness analyses. These data will also be used to estimate costs per quality-adjusted-life-year (QALY) saved, based on prior estimates of QALY associated with smoking status. As recommended by Feirman et al. sensitivity analyses will be conducted, using alternative QALY measures to assess robustness of estimates. We can

use data from the project's factorial design to generate smoothed estimates of the costs per quit and costs per QALY for different combinations, using multivariate regression analysis. We will also estimate potential savings related to reduced smoking levels, as a function of previous smoking frequency and the estimated effects of the interventions on quitting or self-reported post-intervention smoking frequency. This approach could use information from the factorial design to create smoothed estimates of personal savings.

***Data Sources and Collection:*** Participants will self-report health care utilization and spending on tobacco and cessation treatments; Optum will report on WTQL intervention costs; and SmokefreeTXT will report on the volume of text message exchanges and total costs per user. UW-CTRI will collate data from these sources for analyses.

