To assess Aim 3, we will identify demographic and smoking history moderators of treatment engagement and response and mediators of intervention effects (e.g., treatment engagement) on 6-month abstinence. Such analyses examining treatment by moderator interactions or examining treatment effects in subgroups of participants (e.g., the uninsured versus Medicaid-eligible; men versus women) will identify sub-populations that may not benefit equally from enhanced WTQL services using data collected by the WTQL at registration or study enrollment. We will also explore the extent to which treatment engagement (measured throughout counseling and SmokefreeTXT and at follow-up for medication) and cessation motivation and confidence (assessed at follow-up) differed across treatment conditions, and the extent to which such differences may mediate or account for treatment effects on abstinence.

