***Measures, Populations and Analysis:***

Self-report demographic, smoking history, health status, psychiatric history, and texting use collected at WTQL registration or study enrollment will be examined as candidate moderators of treatment response. Mediators (treatment engagement; perceived support; reduction in exposure to smoking/triggers; quitting motivation and confidence) will be assessed during treatment (in the case of treatment engagement) or during follow-up telephone interviews at 12- and 26-weeks post-quit.

The population will be the eligible, consented, enrolled subjects who were randomized to treatment. Participants who were randomized but did not complete the study will be included (unless they requested that their data not be used upon withdrawal from the study). Analyses will occur in the full intent-to-treat sample whenever possible, using model estimation that permits missing data.

Evaluation of moderators will be accomplished with moderated logistic regression models that include effect-coded intervention main and interaction effects on abstinence, a given moderator, and interactions of the moderator with the intervention effects. Mediation analyses will include linear regression models in which mediators are regressed on intervention main effects and interactions, logistic regression models in which binary abstinence outcomes are regressed on both intervention variables and mediators, and estimates of the mediated effect. Formal mediation analysis computed via the SAS PROCESS macro.

***Data Sources and Collection:*** Candidate moderators will be assessed via participant self-report by the WTQL during initial registration or study enrollment. Treatment engagement mediators will be assessed by the WTQL (for counseling completion), SmokefreeTXT (for SmokefreeTXT completion and interactions), and by UW-CTRI at follow-up telephone interviews (for self-reported patch and mini-lozenge use). Other candidate mediators

(cessation motivation and confidence) will be assessed by UW-CTRI during 12- and 26-week telephone follow-up interviews.

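### Aim 3 asks who benefits unequally, but its only specified moderator test compares odds ratios, and no risk-difference contrast by subgroup is planned

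*Combined protocol and SAP*

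**What the plan says.** In II. GOALS/AIMS, Aim 3 is given this purpose: "This aim will identify sub-populations that may not benefit equally from enhanced WTQL services". The Aim 3 part of the Analysis Plan says again that the analyses "will identify sub-populations that may not benefit equally from enhanced WTQL services". It mentions treatment-by-moderator interactions or, as an alternative, "examining treatment effects in subgroups of participants (e.g., the uninsured versus Medicaid-eligible; men versus women"), without naming an effect scale for the subgroup effects.

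The Aim 3 Measures, Populations and Analysis text gives the one specified method: "Evaluation of moderators will be accomplished with moderated logistic regression models that include effect-coded intervention main and interaction effects on abstinence", plus the moderator and its interactions with the intervention effects. For Aim 1 the Analysis Plan says: "Logistic regression analyses will be used to estimate intervention main and interactive effects on binary abstinence outcomes". Neither aim commits to a risk difference, a standardized abstinence rate or an interaction on the additive scale.

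The project's intended uses are stated in absolute terms. The Significance section promises: "This evaluation will identify which program enhancements, and which combination of program enhancements, improve abstinence rates". Under Aim 2, cost and abstinence data "will be used to estimate the costs per verified quit by treatment condition". Aim 2 does not plan this by moderator subgroup.

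**The concern.** A product term in a logistic model tests whether the odds ratio is the same in each subgroup. A quit line planner deciding whether a group is underserved needs to know how many more people per hundred quit. The two questions have the same answer only when underlying quit rates are similar.

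There is reason to expect that they differ. The candidate moderators are demographics, smoking history, health status, psychiatric history and texting use. The Significance section itself says that quitting success varies with socioeconomic position.

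Aim 3 could then report no moderation where one subgroup gains clearly fewer quits, or report moderation where the gains are the same. Because the plan does not fix the scale on which benefit is to be described, that choice could also be made after the results are seen.

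**Working it through.** **Inputs.** From the documents: target sample 1,408–1,600 (Recruitment section) and the logistic moderator model (Aim 3). The documents give no quit rate, odds ratio, alpha or power, so there is no stated figure to reproduce. Control rates of 5–30% and odds ratios (OR) of 1.3–2.0 are assumptions.

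**Step 1: equal odds ratios, unequal quits.** With control rate p0, the treated rate is p1 = OR·p0 / (1 − p0 + OR·p0), and the gain is p1 − p0. At OR = 1.5:

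- p0 = 6%: 0.09 / 1.03 = 8.74%, gain 2.74 points.
- p0 = 14%: 0.21 / 1.07 = 19.63%, gain 5.63 points.

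The logistic product term is exactly zero, yet the second group gains 2.05 times as many quits.

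**Step 2: range.** Nine pairs of control rates were tried: 5/10, 5/12, 6/12, 8/16, 10/15, 10/20, 15/25, 15/30 and 20/30%. Within a pair the rates differ 1.5- to 2.4-fold.

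| Common OR | Smallest ratio of gains (20% vs 30%) | Largest ratio of gains (5% vs 12%) |
|---|---|---|
| 1.3 | 1.28 | 2.18 |
| 1.5 | 1.26 | 2.15 |
| 1.8 | 1.23 | 2.11 |
| 2.0 | 1.21 | 2.08 |

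A two-fold gap lies near the top of this range. At OR 1.5 a group at 5% needs a comparison group at about 11%, one at 8% needs about 19%, and one at 10% needs about 26%. From 15%, no comparison rate up to 60% gives a two-fold gap at the ORs searched (1.3, 1.5 and 2.0). Pairs further apart than those in the table would give larger ratios.

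**Step 3: equal quits, unequal odds ratios.** Let both groups gain 4 points.

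- 6% to 10%: (0.10/0.90) / (0.06/0.94) = 1.74.
- 14% to 18%: (0.18/0.82) / (0.14/0.86) = 1.35.

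The ratio of odds ratios is 1.74 / 1.35 = 1.29, which the logistic model counts as moderation.

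**Step 4: the order can reverse.** OR 1.7 at 6% gives 0.102 / 1.042 = 9.8%, a gain of 3.8 points. OR 1.4 at 14% gives 0.196 / 1.056 = 18.6%, a gain of 4.6 points. The group with the larger odds ratio gains fewer quits.

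**Step 5: precision of a risk-difference contrast.** Take the Step 1 example with two equal subgroups, one factor, every participant given an outcome and a two-sided 5% test. There are four groups of N/4.

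- Difference in gains: 5.63 − 2.74 = 2.89 points.
- Sum of p(1 − p): 0.0564 + 0.0797 + 0.1204 + 0.1577 = 0.4143.
- N = 1,600: SE = √(0.4143/400) = 3.2 points; 2.89/3.22 = 0.90; power about 15%.
- N = 1,408: SE = √(0.4143/352) = 3.4 points; 2.89/3.43 = 0.84; power about 13%.

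The 95% interval has a half-width of about 1.96 × 3.2 = 6.3 to 1.96 × 3.4 = 6.7 points.

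**The case against.** The strongest reply is that changing the scale would seldom change a test result. With power of 13–15%, the risk-difference contrast would usually be null too. In the equal-gain example of Step 3, the logistic product term would be significant only about 11–12% of the time. This stands, and it is why the remedy lies in estimates and intervals rather than in a different test. It does not remove the need for an estimate in the units of the question.

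A second reply is that a logistic model fixes the fit, not the reported measure. The subgroup effects mentioned under Aim 3 carry no stated scale, and nothing in the text says that a null product term will be reported as equal benefit. All of this is true. The gap is one of commitment: nothing obliges the analysts to report absolute contrasts by subgroup.

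Three stronger readings are tempting, and the documents do not support them:

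- **The best combination is judged only on the odds-ratio scale.** Aim 2 plans cost per verified quit by condition and says smoothed estimates for different combinations can be produced; both depend on absolute quits. Ranking the 16 cells from one unadjusted fit gives the same order on either scale.
- **A package's predicted quits, and so its cost per quit, shift with the scale by some fixed factor.** That would require a model without factor interactions. The Aim 1 text includes the interactions; with all of them in an unadjusted model, fitted cell rates equal observed rates under any link.
- **The mediation results are biased by the logistic scale.** That would require mediation to be judged by comparing direct with total log-odds effects, and the plan does not say so.

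**Conclusion.** The point holds for Aim 3. The only specified moderator test is on the odds-ratio scale, the question is about who benefits less, and no absolute contrast by subgroup is planned. The mechanism is arithmetic; its size here is unknown because the documents give no quit rates. For control rates that differ 1.5- to 2.4-fold within 5–30% and a common odds ratio of 1.3–2.0, quits gained differ by a factor of about 1.2 to 2.2. A reader might infer that a two-fold disparity would be missed, but that is the upper part of an assumed range and not a prediction for this trial. If subgroup quit rates prove similar, the two scales will agree closely.

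This is a worthwhile pre-specification of reporting and does not show the logistic model to be wrong. Making the risk scale the sole basis for conclusions would be debatable, and the documents do not compel it.

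**What to change.** Keep the logistic models and add the following to the Analysis Plan.

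- From the same fits, compute model-standardized abstinence rates and risk differences with confidence intervals (delta method or bootstrap) for each main effect, each two-way interaction and each moderator contrast.
- Report these beside the odds ratios.
- Base statements about equal or unequal benefit on the risk-difference contrasts and their intervals as well as on the logit product term.
- State that a non-significant interaction on either scale will not be described as equal benefit.

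The cost is a little more analysis output. No new data are needed and the models do not change. The intervals on moderator contrasts will be wide, and the report should say so.

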### **D. Randomization**

Randomization will occur immediately after baseline data are collected after oral consent is obtained and will be conducted by WTQL staff using randomization tables developed at UW-CTRI. Randomization will be blocked by ethnicity and race to ensure an even distribution of participants of these factors that may relate to intervention success. Enrollees will be randomized to one of 16 conditions, as shown above. No placebo will be used in this real-world trial. Every enrollee will receive no less than the current standard in WTQL care, a single counseling session, a 2-week supply of a single nicotine replacement therapy (if medically eligible for nicotine medication), and unlimited access to a WTQL Quit Coach by request.

Following randomization, WTQL staffers will describe the randomized interventions in accessible language. This will include description of the counseling offered; description of the medications to be mailed to the participant; information about SmokefreeTXT; and a description of relevant incentives and their contingencies (i.e., \$30 for each counseling call lasting, \$30 for staying in SmokefreeTXT for the full 6 weeks post-quit).

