Optum will give participants randomly assigned to SmokefreeTXT who agree to receive information about SmokefreeTXT instructions about how to enroll. In turn, ICF International will transmit results data from SmokefreeTXT via secure FTP to help staff at Optum determine whether or not a participant has earned the \$30 incentive for staying enrolled in SmokefreeTXT through 6 weeks post-quit day.

UW-CTRI will receive data on enrollees to facilitate follow-up assessments. These data will include a study identifier and contact information (name, telephone number, address) needed to conduct telephone interviews and to find the nearest UW-CTRI office for biochemical verification of claims of abstinence at the 26-week follow-up. UW-CTRI staff who conduct follow-up interviews and verification will be blind to study condition and will not have access to other participant data (e.g., smoking history) prior to the end of data collection. All data transmissions to and from UW-CTRI will occur via secure FTP.

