### **Assessment Plan**

1. Baseline assessment (See uploaded registration data from the WTQL). Specific fields collected at initial registration for WTQL services will be pulled for study use and analyses. These items include age; gender; race; ethnicity; county; education; insurance status (uninsured, in BadgerCare Plus/Medicaid, or privately insured (if low in education)); chronic health conditions; registration date; how heard about WTQL; and smoking history (multiple items). These data will be collected for all consented enrollees and patient-level data without direct identifiers will be collected for those who are unreachable, are ineligible, or decline to enroll.
2. Enrollment assessment (see uploaded Post Consent Baseline assessment). Following oral consent, additional data that are not routinely assessed at the standard post-WTQL enrollment follow-up will serve as baseline assessments for the evaluation study. Items include a detailed assessment of smoking in the past 7 days (how many cigarettes smoked on each day) and other current eligibility criteria. In addition, items will assess supplemental indicators of socioeconomic status, recent use of nicotine products and smoking cessation therapies and associated costs, use of healthcare over the past 6 months (for cost-effectiveness analyses), frequency of texting, indicators of relapse proneness, brief psychiatric

status/history screener (without questions on illicit substance use), and menthol cigarette use. The WTQL will also confirm registration data whenever someone re-enrolls in treatment, as per their standard protocol. The target quit date will also be collected.

3. Engagement assessment. Engagement will be tracked using data routinely collected in the course of existing services, including the number and duration of WTQL calls completed and use of the WTQL Text2Quit program (among 18-24 year olds who enroll in this program outside of their study enrollment call, which is possible), the duration of enrollment in SmokefreeTXT and the number and content (e.g., craving or mood ratings; smoking status reports; requests for help with craving, mood, or slips) of inbound, subject-generated messages to SmokefreeTXT. Medication use will be assessed via self-report at 12- and 26-week follow-up telephone interviews.

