Optum, the WTQL vendor, employs physicians to review medication protocols and has a rigorous adverse event monitoring protocol. All medications will be dispensed in ways that are consistent with the protocol and packaging instructions, with clear instructions. No more than a 4-week supply will be provided. Participants experiencing side effects will be advised to seek local

medical care as needed, with the understanding that the costs of the medical care will be the responsibility of the participant (or the participant's insurer), as discussed in the consent process.

The risk of aversive withdrawal symptoms will be addressed in two ways. First, standard WTQL practice addresses the nicotine withdrawal syndrome in an individually tailored manner. This will not change in the current study. Second, we will provide nicotine replacement to all participants, in accordance with best practice and current practices at the WTQL. All participants will be advised that they can call the WTQL for additional coaching calls, as needed, so even those in the single-scheduled-counseling-call-condition will have access to ongoing support regarding the management of nicotine withdrawal. Everyone medically eligible for NRT will receive at least nicotine patches (and half will receive lozenges in addition to patches) to address withdrawal during the first 2-4 weeks of the smoking cessation effort.

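### Aim 3's engagement mediation for SmokefreeTXT and counseling pairs a nearly guaranteed first path with a confounded second path, so it can show a mechanism for a component with no effect

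*Combined protocol and SAP*

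**What the plan says.** Aim 3 (Analysis Plan) will explore whether engagement, motivation and confidence differ across conditions, and "the extent to which such differences may mediate or account for treatment effects on abstinence". The method, under Measures, Populations and Analysis for that aim, is a linear regression of each mediator on the intervention main effects and interactions, followed by "logistic regression models in which binary abstinence outcomes are regressed on both intervention variables and mediators, and estimates of the mediated effect", computed with the PROCESS macro.

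The engagement measures (Assessment Plan, item 3) are the number and length of completed quitline calls, "the duration of enrollment in SmokefreeTXT and the number and content" of inbound texts, and self-reported medication use. The factors that supply these services (Goals/Aims table) are "1 vs. 4 proactive counseling calls", SmokefreeTXT as "Proactive enrollment vs. none", and NRT intensity. Incentives are different: they pay for engagement, including "staying enrolled in SmokefreeTXT through 6 weeks post-quit day" (section G), but do not supply the service.

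Two passages limit how far assignment fixes call use. Every enrollee has "unlimited access to a WTQL Quit Coach by request" (section D), and section H adds: "All participants will be advised that they can call the WTQL for additional coaching calls, as needed".

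The paragraph on mediation names no baseline confounders, no sensitivity analysis for unmeasured confounding, and no condition that the factor affect abstinence overall. The adjusted models in the Analysis Plan belong to Aim 1.

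**The concern.** A mediated effect is the product of two paths. Randomization protects the first, from factor to engagement. It does not protect the second, from engagement to abstinence with the factor held fixed, because nobody was randomized to stay in the text program or to take more of the calls offered. More motivated or less dependent people may do both, and people who relapse early may stop texting and stop answering calls. Either pattern produces a positive second path when engagement does nothing.

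For texts and calls the first path is close to guaranteed, so it gives no protection: the product is significant whenever the confounded path is. Aim 3 is meant to suggest how treatments might be refined, and mediation is to have its own manuscript. A component with no effect could be presented there as working through engagement.

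**Working it through.** The documents give no abstinence rate, alpha, effect size or mediation figure, so there is no stated result to reproduce. The check has two parts.

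**1. What the model estimates.** Let X be the text factor (0/1), M SmokefreeTXT engagement and Y abstinence:

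- M = a0 + a·X
- logit P(Y=1) = i + c′·X + b·M
- mediated effect = a·b

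If M is 0 throughout the no-text cells, those cells determine only i. The text cells determine i + c′ and b. So b is exactly the slope of abstinence on engagement among people assigned to texts, and a is their mean engagement. If the text program has no total effect, then c′ ≈ −a·b: a spurious benefit through engagement is balanced by a spurious direct harm. For calls, b is the pooled slope within the 1-call and 4-call levels, which is again a self-selected comparison.

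**2. How often this gives a false mechanism.** Inputs from the documents: N = 1,408 to 1,600; 16 cells, so 1,408/16 = 88 to 1,600/16 = 100 per cell, and 704 to 800 per factor level; the regressions above. Assumptions not in the documents:

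- no factor affects abstinence;
- abstinence is 12% (range 6-20%);
- text engagement is 0-6 weeks in the text cells and 0 elsewhere;
- scheduled calls taken are 0-1 or 0-4, plus about 0.2 on-request calls per person;
- one unmeasured trait raises engagement (log-odds 1 per SD) and abstinence (odds ratio, OR, as tabulated).

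Results for the full 2^4 model, N = 1,408, 1,500 trials per row, with a 95% Monte Carlo interval for a·b (nominal two-sided error 5%):

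| Trait OR per SD | Interval excludes 0: text / calls | Mean apparent mediated OR: text / calls | Total-effect test rejects: text / calls |
|---|---|---|---|
| 1.00 | 4.3% / 5.2% | 1.00 / 1.00 | 5.4% / 4.9% |
| 1.22 | 24.4% / 24.5% | 1.35 / 1.18 | 5.3% / 6.5% |
| 1.49 | 71.5% / 73.6% | 1.81 / 1.38 | 5.3% / 4.9% |
| 2.01 | 99.4% / 99.5% | 2.78 / 1.72 | 4.8% / 5.7% |

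From OR 1.22 upward, essentially all the false results are in the beneficial direction. At OR 1.49:

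- N = 1,600: 76.9% / 79.3%.
- Abstinence 6%: 45.4% / 47.3%; abstinence 20%: 86.0% / 87.5%.
- Calls with no on-request calls at all: 75.7%, against 73.6% with them.

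A simpler model gives the same picture: text factor only, 15% abstinent, M = 6·expit(0.5 + U + e) in the text arm with U the trait, and a Sobel z above 1.96 (nominal 2.5%). False beneficial mediation occurs in 24%, 71% and 96% of trials at OR 1.22, 1.49 and 1.82. Repeat runs gave 26%, 70% and 97% for text, and 23%, 69% and 96% for calls. At OR 1.49 the mean indirect OR is 1.94 and the direct OR 0.50; 1.94 × 0.50 = 0.97, close to the true total of 1. A test based on assignment alone stayed at 2-4%.

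**What reduces the error** (full model, OR 1.49, text / calls):

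- Adjust both paths for the trait measured perfectly: 4.7% / 5.4%.
- Adjust for a proxy of reliability 0.5: 26.7% / 31.7%.
- Count a mediated effect only if the total effect is also significant: 3.9% / 3.9%.

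**The case against.** The strongest reply is that the fault is ordinary confounding and not the structural link between factor and engagement. That is right. A reader might infer that a factor which supplies its own mediator must produce a false mechanism. The first row of the table shows that it does not: with no shared trait, the error is 4.3% and 5.2%. The structural link only removes the protection that an uncertain first path would give.

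Other strong readings also fail on the documents:

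- *Calls are limited to 1 or 4.* Only proactive calls are. On-request calls are open to all, and the engagement measure counts completed quitline calls.
- *Texting is zero without the text factor.* This holds for SmokefreeTXT as assigned. Text2Quit use by 18-24 year olds is possible and tracked.
- *Assignment fixes NRT use.* Patches go to medically eligible people at both levels, so patch use can vary at both.
- *The text incentive is earned just by not opting out.* Participants must first agree to receive information and then enroll.
- *Incentive mediation is safe because incentives do not define engagement.* The question is sensible, but the second path is the same. Suppose incentives raise the share of service used by 7 to 18 points and have no effect on abstinence. With 15% abstinence and trait OR 1.49, false mediation appears in 53-68% of trials for text share (n = 704) and 92-96% for call share (n = 1,408).

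It is also fair that Aim 3 is described as exploratory and that Aim 1 reports each component's intent-to-treat effect, so a null component would be visible to a reader who looks at both. This lowers the stakes. It does not correct the mediated estimate, and nothing in the plan ties the mediation report to the Aim 1 result.

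**Conclusion.** The concern holds in this form. For SmokefreeTXT and counseling, the stated mediation analysis combines a nearly guaranteed first path with a second path open to confounding. If engagement and quitting share a cause, Aim 3 can report a beneficial mediated effect for a component that does nothing. For text, the false-positive rate is about 24-26% at a trait OR of 1.22 per SD and about 70% at 1.5, with similar rates for calls.

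The trait strength, abstinence rate and engagement model are assumptions. They determine the size of the problem. Its direction needs only that a common cause of persistence and quitting exists, and without one the error is nominal. The incentive analysis has the same weakness in its second path.

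A reader might also infer that the trial's main result is compromised. It is not: Aim 1 compares randomized groups and does not use engagement. The plan should be changed before the mediation analysis is run, but the primary analysis does not depend on it.

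**What to change.** In the Aim 3 paragraph on moderators and mediators (Measures, Populations and Analysis):

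1. **SmokefreeTXT.** Replace engagement mediation with the intent-to-treat effect plus a complier-average (instrumental-variable) effect. Use random assignment as the instrument and state the definition of uptake in advance.
2. **Counseling and NRT.** Report the intent-to-treat effect and describe engagement by condition, also as a share of what was offered. Uptake has no single clear definition here (1 vs 4 scheduled calls plus on-request calls; patches at both NRT levels), so a complier-average effect is not proposed.
3. **Incentives and any other mediation kept.** Adjust both paths for baseline smoking history, relapse-proneness and other baseline covariates already collected. Add a sensitivity analysis for unmeasured mediator-outcome confounding, because an imperfect proxy left 27-32% false positives above. Claim a mechanism only when the factor's total effect on abstinence is also supported. That condition guards against mechanisms for null components; it does not remove bias from the mediated estimate, so the sensitivity analysis is needed as well.

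The cost is plan wording and some extra analysis on data already collected. The complier-average interval will be wider than the intent-to-treat interval, and it rests on the exclusion assumption that assignment affects abstinence only through uptake. Fewer mechanism claims will be possible.
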